3.5.2. Standard Oncology Care

Participants assigned to the control arm will receive standard oncology care provided by their oncologist and will not have any further contact with the study doctor following randomisation. The treating clinicians will be blinded to the results of any study assessments. Assessments of outcome measures occur at 12 weeks, 18 weeks and 24 weeks following randomisation. After 24 weeks, participants will no longer be required to complete further study assessments. Although participants in the control arm may be referred to a geriatrician at any time by their treating clinicians, they will not be permitted to cross-over to receive the study-specific comprehensive geriatric assessment and management.

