1.3.2. Potential Study Risks

The risks associated with this research are comparatively small and relate to the potentially distress that may be caused by some of the items within the questionnaire.

2. Study Objectives

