3.3. Recruitment

Participation in the study will be completely voluntary. Potential participants will be referred by their treating clinicians to the researcher and, if interested, they will be provided with a Participant Information and Consent Form (PICF) and given sufficient time to consider whether or not to participate in the study. If they are willing to participate in the study, participants will be requested to sign the PICF and an optional Medicare Australia participant consent form. Once a participant has consented, participants will be screened for suitability according to the inclusion and exclusion criteria (refer to **3.2.1.** and **3.2.2.**). If they are suitable to participate in the study, the study doctor will perform the baseline assessment prior to treatment allocation. All participants will also receive brief generic advice about nutrition and activity and will be given the Cancer Council of Victoria's booklet on "Understanding Chemotherapy: a guide for people with cancer, their families and friends".(50) The provision of generic information prior to treatment allocation is being performed to reduce any non-specific therapeutic effect of seeing the study doctor and to encourage patients to continue with the study regardless of treatment allocation.

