The remainder of the assessment and development of the management plan must include a personal attendance by the study doctor. This attendance should include performance-based assessment of cognition by Montreal Cognitive Assessment (MoCA). A prioritised list of diagnoses/problems will be developed based on the information derived from the history and examination, and any additional information provided by other means, including an interview of a person other than the patient.

The management plan will be individualised to the patient's needs and may include:

- measures to optimise concurrent health issues
- medication recommendations
- non-medication recommendations (e.g. lifestyle changes, including exercise and diet)
- assessment of the risk of chemotherapy toxicity
- referrals to relevant existing hospital and community services (e.g. allied health services, rehabilitation services, aged care services, palliative care services)

The management plan should be explained and, if necessary, provided in written form to the patient or, where appropriate, their family or carer(s). A written report of the comprehensive geriatric assessment and management plan will be communicated back to the treating oncologist and general practitioner within a maximum of 2 weeks of the assessment via email or mail. More prompt verbal communication may be appropriate.

Participants assigned to the intervention arm will receive a comprehensive geriatric assessment and management within 3 weeks of randomisation. Participants assigned to the intervention arm will continue to see their oncologists who are the participants' primary physician for treatment of their cancer and related health conditions. Further reviews with the study doctor will occur at approximately 12 weeks and 24 weeks after randomisation. The 12 weeks and 24 weeks reviews should include performance-based assessment of functional mobility by TUG. Additional reviews with the study doctor may be scheduled as required depending on medical needs.

Assessments of outcome measures occur at 12 weeks, 18 weeks and 24 weeks following randomisation. After 24 weeks, participants in the intervention arm may continue to receive integrated geriatric care but will not be required to complete further study assessments.

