3.6.5.2. Study Day 0 (Baseline Assessment)

Day 0 is defined as the day of enrolment and administration of baseline assessment. Study participants must sign the informed consent form and complete baseline assessment to be considered enrolled into the study. At the baseline assessment, participants complete a series of PRO measures (see **3.6.1.**) and the timed-up-and-go test (TUG) (refer to **Appendix 12A**). The time required to complete the PRO measures at baseline assessment is approximately 13 minutes. The time required to complete the TUG is approximately 2 minutes.

The researcher will also collect additional data regarding participant characteristics, disease characteristics, comorbidities and medications (see **3.6.1.**).

Treatment allocation will occur after the informed consent form and baseline assessment has been completed. For participants assigned to the intervention arm, the results of the baseline assessment (except the HRQoL questionnaires because it will be used to calculate the primary outcome measure) will be made available to the treating clinicians. For participants assigned to the control arm, treating clinicians will be blinded to the results of the baseline assessment.

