3.6.5.4. Study Week 12, Week 18 and Week 24 (follow-up assessments)

Follow-up assessments are evaluated at 12 weeks, 18 weeks and 24 weeks after randomisation. Assessments are permitted within the 3 weeks period prior or 3 weeks period following the assessment time-point, with preference for assessment to be done immediately before a specified treatment cycle where possible. To avoid more frequent clinic visits, the researcher will make an effort to meet with participants at their regularly scheduled visits, such as appointments with their oncologists and chemotherapy or radiotherapy sessions. At the scheduled assessment timepoints, all participants will be asked to complete a series of PRO measures (see **3.6.1.**). The times required to complete the PRO measures at week 12 is approximately 13 minutes; week 18 is approximately 3 minutes; and week 24 is approximately 13 minutes.

The researcher will also collect additional data regarding participant characteristics, disease characteristics, comorbidities, medications, chemotherapy delivery, healthcare utilisation, level of care and survival (see **Section 3.6.1.**).

For participants assigned to the intervention arm, the results of the follow-up assessments (except for the HRQoL questionnaires) will be made available to the treating clinicians. For participants assigned to the control arm, treating clinicians will be blinded to the results of the follow-up assessments.

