3.6.6. Reporting Requirements for Missing Data

In addition to protocol-specific assessments completed by participants, the researcher will complete a compliance form for each scheduled assessment – the INTEGERATE Completion and Missing Data (CoMiDa) form (see **Appendix 13**). This form will document whether the assessments were completed and the circumstances in which they were completed. If a study participant does not complete a questionnaire, the researcher will document the reason for non-completion on the CoMiDa form. The information on missing data will be used in two ways. First, during study implementation, the information on missing data will be used to monitor rates and reasons for missing PRO data in real time to allow remedial intervention to correct administrative oversights and errors in PRO questionnaire administration. Second, the information on missing data will be used in the analysis to describe missing data patterns and to explain variability in outcomes.

Some sources of missing data cannot be avoided, such as attrition due to death and withdrawal due to progressive disease and toxicity. Other sources of missing data are considered avoidable and may be due to administrative oversights and errors in PRO questionnaire administration. Accurate records of both avoidable and unavoidable sources of missing data will be documented using the CoMiDa form.

The following approaches will be used to minimise avoidable missing PRO data: 1) PRO assessments should be administered on schedule and within allowable time windows; 2) the circumstances related to late or non-completion will be monitored (via the CoMiDa Form); and intervention should be taken to correct administrative oversights and errors in PRO questionnaire administration.

In particular, if an assessment or part of an assessment is missed, an attempt should be made to contact the participant to complete the assessment. Where possible, the participant should complete the assessments in person. If this is not possible, the questionnaire may be mailed to them with a reply paid envelope. Up to three reminder telephone calls will be made by the researcher to encourage the participant to complete and return the questionnaires by post.

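### Control-arm clinicians are blinded to PHQ-9 and GAD-7 with no specific exception for a severe score, and at weeks 12 and 24 no role in the supplied text is assigned to score one or pass it on

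*Combined protocol and SAP*

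**What the plan says.** PHQ-9 and GAD-7 are scheduled in both arms at baseline, week 12 and week 24 (protocol 3.6.1; SAP 2.5.1). Participants complete them on paper without help from site personnel (protocol 3.6.3). Protocol 3.7.3.4 and SAP 2.7.2.4 place the severe band at 15, put the cutpoint for further evaluation and treatment at 10, and say that 9 or less needs no action.

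The control-arm rule appears in four places. Protocol 3.5.2 says "The treating clinicians will be blinded to the results of any study assessments", and SAP 2.4.2 repeats it. Protocol 3.6.5.2 says "For participants assigned to the control arm, treating clinicians will be blinded to the results of the baseline assessment". Protocol 3.6.5.4 says "For participants assigned to the control arm, treating clinicians will be blinded to the results of the follow-up assessments". None of these carries an exception.

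Before allocation, "the study doctor will perform the baseline assessment prior to treatment allocation" (protocol 3.3). Afterwards control participants "will not have any further contact with the study doctor following randomisation" (protocol 3.5.2).

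In the intervention arm, all follow-up results except the HRQoL questionnaires are made available to treating clinicians (protocol 3.6.5.4). In addition, "Further reviews with the study doctor will occur at approximately 12 weeks and 24 weeks after randomisation" (protocol 3.5.1).

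**The concern.** The trial administers two mood screens, cites the score at which evaluation and treatment are recommended, and then withholds the result from the control participant's treating clinicians. Protocol 1.3.2 says that the study's risks "relate to the potentially distress that may be caused by some of the items within the questionnaire", but it gives no rule for handling a high score.

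The stated reason for withholding results applies only to the HRQoL questionnaires, because they generate the primary outcome (protocol 3.6.5.2). The documents give no reason for withholding a severe mood score.

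At stake is the individual patient. Whether a control participant's severe score at week 12 or 24 reaches a doctor depends on someone happening to see it and choosing to use a general permission. The same score in the intervention arm has a written route to a clinician.

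**Working it through.** **Who could see a control-arm mood score, and what the text asks of them**

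- *Treating clinicians:* blinded at baseline and follow-up (protocol 3.5.2, 3.6.5.2, 3.6.5.4; SAP 2.4.2).
- *Study doctor:* performs the baseline assessment in both arms (3.3), but is given no duty to act on a control participant's mood forms. No contact with controls after randomisation (3.5.2).
- *Researcher:* meets participants at follow-up (3.6.5.4), chases missed parts of assessments and fills in the CoMiDa form (3.6.6). Of that form the protocol says "This form will document whether the assessments were completed and the circumstances in which they were completed". This is a completeness record; no scoring task is given.
- *Trial Management Committee:* monitors participant safety (5.1), but no individual score is routed to it.
- *Anyone, under general clauses:* 6.1 allows a deviation to eliminate immediate hazard, and 6.3 allows disclosure to a personal physician for treatment. Both require that someone has already seen the score.

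So at weeks 12 and 24 no listed role has the task of totalling or forwarding a control participant's score. Baseline is different, because a doctor is present.

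**Time to the next screen.** With windows of +/- 3 weeks (3.6.2), the week-12 form falls in weeks 9 to 15 and the week-24 form in weeks 21 to 27. The gap is (21 - 15) to (27 - 9), or 6 to 18 weeks. No study screen follows week 24 (3.6.5.5).

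**The plan's sample size.** A two-sided t-test at 0.05 with 80% power and an effect of 0.5 SD gives 63.77 per group, rounded up to 64; power at 64 is 0.801. This reproduces protocol 4.2.

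**Expected severe scores.** The documents give no prevalence, so p is an assumption. At one screen with n = 64, the expected number is 64p and the chance of at least one is 1 - (1 - p)^64.

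| Assumed p | Expected | Chance of at least one |
|---|---|---|
| 0.25% | 0.16 | 15% |
| 0.5% | 0.32 | 27% |
| 1% | 0.64 | 47% |
| 2% | 1.28 | 73% |
| 5% | 3.2 | 96% |

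Even odds fall at p = 1 - 0.5^(1/64) = 1.08%.

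**Workload.** Control form pairs: 64 x 3 = 192. Both arms: 384. At an assumed 1 to 3 minutes per pair, 192 pairs take 3.2 to 9.6 hours and 384 take 6.4 to 19.2 hours. The 64 is a minimum of participants who completed both baseline and week 12, so attrition means more baseline forms.

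**Dilution of the 12-week contrast.** A score released at week 12 follows that visit's questionnaires, so only baseline releases can affect the 12-week comparison that sized the trial. Week-12 releases could affect weeks 18 and 24. Contrast = 0.5 - (share released x gain per released control), with both terms assumed:

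| Share released | Gain | Contrast | Power at 64 per group |
|---|---|---|---|
| none | - | 0.50 SD | 80% |
| 1% | 0.5 SD | 0.495 SD | 79% |
| 5% | 0.5 SD | 0.475 SD | 76% |
| 1% | 1.0 SD | 0.49 SD | 79% |
| 5% | 1.0 SD | 0.45 SD | 71% |

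These rows are illustrations, not bounds. A trigger of 10 would release more. For example, 10% released with a 0.5 SD gain gives 0.5 - 0.05 = 0.45 SD, again 71%.

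**The case against.** The strongest objection is that this is an argument from absence. The consent pages were removed and Appendix 9, which holds the mood forms, was not supplied. Either could contain an escalation step, and protocol 6.2 sends the protocol and consent forms to ethics review together. This stands: if such a step exists there, the point falls away.

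A reader might infer that the protocol forbids passing on a severe control-arm score. The documents do not support that. Section 6.1 overrides any rule where there is immediate hazard, and section 6.3 permits disclosure for treatment. Section 3.5.1 also names the general practitioner separately from the treating oncologist, so blinding of treating clinicians arguably leaves the general practitioner route open. What is missing is a reader and a trigger, not permission.

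A reader might also infer that low mood in controls would go undetected. That does not follow either. Controls keep their oncologist and can be referred to a geriatrician at any time (3.5.2). Nor does the intervention arm have a severe-score trigger; it has open results and scheduled reviews.

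It can also be said that control-arm blinding is deliberate and protects the contrast, and that no estimand, alpha or sample size is affected. Both are true. They argue for a narrow exception rather than none, since the stated reason for withholding covers only the HRQoL questionnaires.

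Finally, the assumed prevalence range is too wide to settle how often this would arise. That is fair; it shows only that alerts at 15 would be few across that range.

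**Conclusion.** The point holds for the supplied text and goes beyond missing detail: following the written rule withholds a severe mood screen from treating clinicians in one arm and makes it available in the other. It is limited to the lack of a specific exception and, at weeks 12 and 24, the lack of an assigned role. It is a patient-safety gap that should be closed, not a flaw in the analysis.

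Its size is small in numbers: 0.2 to 3.2 expected severe scores per control-arm screen if prevalence is 0.25% to 5%. Confidence is medium, because the conclusion depends on pages that were not supplied and on a prevalence that the documents do not give.

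**What to change.** First check the consent form and Appendix 9. If neither contains an escalation step, add one safety exception to protocol 3.5.2, 3.6.5.2 and 3.6.5.4, mirrored in SAP 2.4.2:

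- A researcher other than the allocator, who must stay blinded to outcomes (protocol 3.4.2), totals PHQ-9 and GAD-7 when each form is received.
- Any score of 15 or more goes to the participant's general practitioner or oncologist within a fixed short limit, for example 2 working days. Clinical action rests with that doctor.
- The EORTC questionnaires stay blinded.
- Releases are logged by arm and time-point and reported beside the mood results.

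The sponsor should say why it chooses 15 rather than the protocol's own evaluation cutpoint of 10. The lower trigger would produce more alerts and somewhat more dilution.

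The cost is a short amendment, one log and the staff time shown above: roughly 3 hours for controls only at the low end, and 19 hours for both arms at the high end, with more if attrition adds baseline forms. Sample size and alpha do not change. The downside is slight dilution of the mood contrast and possibly of the primary contrast.

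SAP 2.2 describes recruitment in the past tense. If form collection is over, SAP 3.5.2 and its Table 4 already tabulate the severe category by arm. The only addition is then the number of severe scores released to a clinician, by arm and time-point.

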3.6. Data Collection

3.6.1. Required Forms

The types of data and frequency of their collection are described in the table below. Patient-reported outcome (PRO) measures will be used to assess a range of outcomes, including HRQoL by the EORTC QLQ-C30, QLQ-ELD14; function by self-rated performance status (ECOG, Karnofsky) and daily activities (ADL, IADL); mood by PHQ-9 and GAD-6; nutrition by self-MNA; and social situation. Additional data will be collected by the researcher, including participant demographics, medical history data (including comorbidities as measured by the Charlson Comorbidity Index), medications, level of care, physician-assessed performance status by ECOG and Karnofsky (KPS), CHSA Clinical Frailty Scale and Timed-Up-and-Go test (TUG). End of study data will be collected and will include a summary of participant's care whilst participating on the study and survival status.

Required Forms	Week				
	Baseline	1	12	18	24 / End of Study
PARTICIPANT FORMS					
Participant Information and Consent Form	X				
Medicare Participant Consent Form (optional)	X				
Global Rating of Change		*	X	X	X
EORTC QLQ-C30 v3.0 and QLQ-ELD14	X		X		X
EQ-5D-5L	X		X	X	X
TOI		*		X	
Function – ECOG, KPS, ADL, IADL	X		X		X
Mood – PHQ-9 and GAD-7	X		X		X
Nutrition – self-MNA and G8 Screening Tool	X		X		X
Social situation	X		X		X
RESEARCHER FORMS					
Demographics	X				
Medical History (including Charlson Comorbidity Index)	X				
Concurrent medications	X		X		X
TUG	X				
Physician-rated ECOG and KPS	X				
CHSA Clinical Frailty Scale	X				
Flemish Triage Risk Screening Tool (fTRST)	X				

Level of care	X		X		X
Height	X				
Weight	X		X		X
Blood test results (FBE, UEC)	X				
Chemotherapy treatment			X		X
Healthcare utilisation			X		X
CoMiDa Form	X	X	X	X	X

* Performed only if participant is commencing chemotherapy on day 8 or later

3.6.2. Time Window for Patient-Reported Outcome and Clinical Assessments

It is very important that the PRO assessments are completed within acceptable time limits surrounding the scheduled assessments.

Baseline assessment should be completed at enrolment and must be completed prior to randomisation. The time window for baseline assessment is therefore the time between obtaining consent and treatment allocation.

For the test-retest assessment (week 1), the time window is from 7 days post-baseline assessment to immediately prior to receiving the first dose of chemotherapy.

For the follow-up assessments (week 12, week 18, week 24) and end of study assessment, a time window of up to +/- 3 weeks is allowed

Researcher forms should be completed on the same day as the PRO forms where possible.

3.6.3. Patient-Reported Outcome Assessments

The EORTC QLQ-C30, QLQ-ED14, EQ-5D-5L, self-rated ECOG, self-rated KPS, Katz ADL, OARS IADL, self-MNA, PHQ-9 and GAD-7 are self-administered questionnaires and are to be completed by the participant without the assistance of the site personnel. These questionnaires are to be completed using pen and paper. All questionnaires should be completed before any other study procedures are conducted.

3.6.4. Estimated Time Required for Patient-Reported Outcome Measures

Assessment	Items	Time to administer (min)	Mode of Administration
Global Rating of Change	1	0.5	Self
EORTC QLQ-C30 v3.0	30	5	Self
EORTC QLQ-ELD14	14	3	Self
EQ-5D-5L	6	1	Self
Self-rated ECOG and self-rated KPS	2	0.5	Self
Katz ADL and OARS IADL	2	0.5	Self
Self-MNA	5	1	Self
PHQ-9 and GAD-7	16	3	Self

* Time to administer for patient-reported outcome (PRO) measures is based on using an estimate of 10 seconds per item.

** Time to administer PRO measures at each assessment timepoint will be detailed in **3.6.5**.

3.6.5. Study Procedure

3.6.5.1. Screening (Days -28 to -1)

During this visit, the participant will be thoroughly informed about all aspects of the study, including all scheduled visits and activities, in accordance with applicable ICH guidelines and local and regulatory requirements. Participant eligibility will be assessed and confirmed by the investigator. All the inclusion and exclusion criteria must be met and none of the exclusion criteria may apply. Participants must sign and date the participant informed consent form and optional Medicare Australia participant consent form **prior** to performance of any study specific procedures. The original signed and dated informed consent form(s) must be retained by the investigator in the participant's file and a copy must be provided to the participant.

3.6.5.2. Study Day 0 (Baseline Assessment)

Day 0 is defined as the day of enrolment and administration of baseline assessment. Study participants must sign the informed consent form and complete baseline assessment to be considered enrolled into the study. At the baseline assessment, participants complete a series of PRO measures (see **3.6.1.**) and the timed-up-and-go test (TUG) (refer to **Appendix 12A**). The time required to complete the PRO measures at baseline assessment is approximately 13 minutes. The time required to complete the TUG is approximately 2 minutes.

The researcher will also collect additional data regarding participant characteristics, disease characteristics, comorbidities and medications (see **3.6.1.**).

Treatment allocation will occur after the informed consent form and baseline assessment has been completed. For participants assigned to the intervention arm, the results of the baseline assessment (except the HRQoL questionnaires because it will be used to calculate the primary outcome measure) will be made available to the treating clinicians. For participants assigned to the control arm, treating clinicians will be blinded to the results of the baseline assessment.

